**7. Are all procedures for research purposes only (non-standard or non-standard of care procedures)?**

Yes  No

If no, list the procedures that are performed for research purposes only (non-standard or non-standard of care procedures):

Data collection and analysis are for research purposes only.

**8. Is there a safety monitoring plan for this study?**

Yes  No

**9. Provide a summary of the statistical methods, data analysis, or data interpretation planned for this study. Factors for determining the proposed sample size (e.g., power) should be stated.**

Summary statistics will be calculated and used to describe the treatment groups (70 versus 110 degrees side-cut angles) in terms of all study variables: manifest refraction, corrected and uncorrected visual acuity and LASIK system used (FS200 or intralase). Statistics will be compiled for the one week, one month, three month, six month and 12 month time points post operatively. Paired t-tests will be used to analyze the difference of corrected and uncorrected visual acuity obtained by each group at the post-op time points, as well as the average change from pre-op to post op corrected and corrected visual acuities. In order to provide a statistically significant beta values, a N number of 200 patients will be needed.

IRB\_00074858

Created: 6/23/2014 8:21 PM

IRB\_00074858

PI: [name]

Submitted: 7/28/2014

View: 4.2 Consent Process

**Title:** 70 versus 110 Degrees Side-cut Angles in Femtosecond  
Laser-assisted in situ Keratomileusis

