**6. Study Purposes and Objectives:**

Different side-cut angles have been used in Femtosecond Laser-assisted in Situ Keratomileusis (FS-LASIK), but no study has compared the safety and efficacy of 70 and 110 degrees side-cut angles. We aim to conduct a prospective trial comparing 70 and 110 degrees side-cut angles on same patient undergoing FS-LASIK. One angle will be performed on the right eye and the other on the left eye. The study will evaluate uncorrected visual acuity, best corrected visual acuity, intraoperative, and postoperative complications. By performing different side-cut angles on a same individual will allow a direct comparison of outcomes, minimizing confounding variables. Additionally, the LASIK flap will be performed using either the Abbott Medical Optics Intralase femtosecond laser or the Alcon Wavelight FS200 femtosecond laser.

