**7. Is this a multi-site study, where more than one site needs IRB approval?** Yes  No**8. Background and Introduction:**

Laser-assisted in Situ Keratomileusis has become the preferred corneal procedure to correct certain refractive errors. Technological advances have increased the accuracy and precision of current treatments. One of the major advancements in LASIK has been the introduction of Femtosecond Laser technology for flap creation. Several studies have compared microkeratome and femtosecond laser technology, showing superior accuracy and precision of flap dimensions in the latter.

The Femtosecond Laser technology provides different parameters and settings that can be changed according to the surgeon's preference. One of such parameters is the side-cut angle. Some of the most common side-cut angles used today include 45, 70, 90, and 110 degrees. Previous studies have reported on the visual outcomes of side-cut angles, but head to head comparisons are lacking. Currently, there are no studies comparing the safety and efficacy of the 70 and 110 side-cut angles in FS-LASIK. Information regarding the outcomes and complication rates between these side-cut angles will provide an objective measure that can be used when deciding which one is more suitable in FS-LASIK.

IRB\_00074858

Created: 6/23/2014 8:21 PM

IRB\_00074858

View: 2. Location and Sponsor

PI: [name]

Submitted: 7/28/2014

**Title:** 70 versus 110 Degrees Side-cut Angles in Femtosecond Laser-assisted in situ Keratomileusis

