**5. How will consent be obtained?**

Informed Consent Process (with or without a document)

**6. Describe all the procedures chronologically, from screening/enrollment through study closeout, which will be completed in the research project.**

Patients who are interested and eligible to participate in this study will sign the study informed consent prior to surgery. As is standard for our LASIK cases, they will also be required to watch an informational video, read and sign the "Consent to Have Refractive Surgery" and respond to a brief test concerning its content.

All surgical procedures will be performed according to the surgeons' standard practices. The study outcome measures are standard of care for pre-operative and post-operative evaluation of refractive surgery patients.

All study outcome measures will be evaluated for both eyes at every visit. Patient will be masked as to the treatment they receive in either eye so as not to influence their subjective responses and visual measurements. Post-operative evaluations will be performed at 1 day, 1 week ( $\pm$  3 days), 1 month ( $\pm$  10 days), 3 months ( $\pm$  14 days), 6 months ( $\pm$  1 month), and 12 months ( $\pm$  1 month). Interim examinations may be performed as necessary according to the surgeon's usual care, but are not considered part of the study data.

Patients will be discontinued from the study if, on the day of surgery, both eyes cannot be randomized and operated as per protocol. Patients have the right to withdraw at any time and future medical care will not be influenced by their lack of participation.

Patients will be evaluated with the following procedures:

- Manifest refraction (sphere, cylinder and axis): Pre op and post-op months 1 ( $\pm$  10 days), 3 ( $\pm$  14 days), 6 ( $\pm$  1 month), and 12 ( $\pm$  1 month).
- Uncorrected corrected visual acuity: Pre-op and post-op day 1, week 1, and months 1 ( $\pm$  10 days), 3 ( $\pm$  14 days), 6 ( $\pm$  1 month), and 12 ( $\pm$  1 month) using the Snellen Eye chart
- Best corrected visual acuity: Pre-op and post-op months 3 ( $\pm$  14 days), 6 ( $\pm$  1 month), and 12 ( $\pm$  1 month).
- Pupil size measured in the dark: Pre-op only

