## 6. Risks and Benefits

**1. Describe the reasonable foreseeable risks or discomforts to the participants:**

Risks to study participants are the same as though for any patient undergoing LASIK refractive surgery, including loss of vision, visual side effects, and over- or under-correction.

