**2. Describe the potential benefits to society AND to participants (do not include compensation):**

Evaluation of vision and complications on an individual patient who has undergone 70 degrees side-angle cut in one eye and 110 degrees side-angle cut in the other will afford a greater understanding of the safety and efficacy of using this two common side-cut angulations. There is no direct benefit to participants.

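### Complications by side-cut angle are a stated objective, but the analysis plan has no complication variable or comparison, and findings at interim examinations are excluded from the study data

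*Combined protocol and SAP*

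**What the plan says.** The objectives (Section 1, item 6) state: "The study will evaluate uncorrected visual acuity, best corrected visual acuity, intraoperative, and postoperative complications". The background (item 8) gives the same reason for doing the trial: "Information regarding the outcomes and complication rates between these side-cut angles will provide an objective measure". The benefits statement (Section 6, item 2) repeats it: "Evaluation of vision and complications on an individual patient who has undergone 70 degrees side-angle cut in one eye".

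The statistical methods (Section 4, item 9) say that the two angle groups will be described "in terms of all study variables: manifest refraction, corrected and uncorrected visual acuity and LASIK system used (FS200 or intralase"). The only inferential method is this: "Paired t-tests will be used to analyze the difference of corrected and uncorrected visual acuity obtained by each group", together with the change in acuity from before surgery. Summaries are planned from one week to 12 months, so day 1 is not among them.

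The procedures (Section 4, item 6) list four assessments: manifest refraction, uncorrected acuity, best corrected acuity and pupil size. Item 6 also says "All study outcome measures will be evaluated for both eyes at every visit". Of interim examinations under usual care, it says that they may take place "but are not considered part of the study data".

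**The concern.** The objective and the analysis do not match. Item 9 presents its variables as the complete set, and complications are not among them. They have no definition, no record per eye, no counting period and no planned comparison between angles. The sentence on interim examinations adds to this, because it shuts out one place where a postoperative complication may first be documented.

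A trial run exactly to plan would report acuity by angle and leave the complication question unanswered. If complications are tallied later, the event types and the visits that count would be chosen after the data exist. Events not recorded per eye at the time may also be hard to recover. The background section offers complication rates as a basis for choosing between the angles, so this is a gap in the trial's main purpose.

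**Working it through.** **Step 1: trace each stated outcome through the plan.**

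| Outcome in the objectives | Procedure (item 6) | Study variable (item 9) | Test by angle (item 9) |
|---|---|---|---|
| Uncorrected acuity | yes | yes | paired t-test |
| Best corrected acuity | yes | yes | paired t-test |
| Intraoperative complications | none | none | none |
| Postoperative complications | none | none | none |

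**Step 2: see whether the listed variables stand in for complications.** Section 6, item 1 names the risks as "including loss of vision, visual side effects, and over- or under-correction". Acuity bears on loss of vision, and refraction on over- or under-correction. Both do so indirectly, because a difference in means does not count affected eyes. Visual side effects and intraoperative events have no variable.

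**Step 3: what the interim sentence can remove.** Scheduled visits are day 1, week 1 and months 1, 3, 6 and 12. With 30-day months these are days 1, 7, 30, 90, 180 and 360. The nominal gaps are 7 − 1 = 6, 30 − 7 = 23, 90 − 30 = 60, 180 − 90 = 90 and 360 − 180 = 180 days. An event that is seen and resolved inside one of these gaps falls outside the study data. An intraoperative event, or one still present at a scheduled visit, is not affected by that sentence.

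**Step 4: illustration of what 200 pairs could show.** Item 9 gives 200 patients but no complication rate, so there is no figure of the plan's own to reproduce. All rates below are assumptions, with independent eyes and an exact two-sided McNemar test at 0.05. With event rates p1 and p2, the discordant probabilities are p1(1 − p2) and p2(1 − p1).

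- 8% versus 2%: 0.08 × 0.98 = 0.0784 and 0.02 × 0.92 = 0.0184. Power is 75%.
- 4% versus 2%: 0.04 × 0.98 = 0.0392 and 0.02 × 0.96 = 0.0192. Power is 14%.
- 2% versus 1%: 0.02 × 0.99 = 0.0198 and 0.01 × 0.98 = 0.0098. Power is 4.5%.

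Suppose a share s of events is seen only at interim visits, equally for both angles, so that each rate is multiplied by 1 − s. For 8% versus 2%, power is then 72% (s = 5%), 70% (10%), 55% (30%) or 37% (50%). The documents do not say which share applies. This model shows lost power, not bias.

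**Step 5: why an interval should lead.** If 8 eyes at one angle and 4 at the other had an event, with no patient affected in both eyes, the difference is (8 − 4)/200 = 2.0 points. The paired score (Tango) 95% CI is −1.6 to 6.0 points, and the exact McNemar p is 0.39. Such a result would not show that the angles are equally safe.

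**The case against.** The strongest reply is that the form asks only for a summary of methods, and that the sentence on evaluating all outcome measures at every visit already takes in complications. Descriptive counts by angle would satisfy an objective that says only that complications will be evaluated. Part of this stands: the objective does not call for a hypothesis test, so a McNemar test is optional. But counts by angle are not planned either. Even on the generous reading, no event is defined, no comparison is stated, and an intraoperative event does not arise at a follow-up visit. The every-visit sentence cannot be taken literally in any case, since best corrected acuity is listed after surgery only at months 3, 6 and 12.

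It is also fair to say that only the objectives section states an objective, and that the background and benefits sections merely support it. The amount lost through the interim sentence is unknown and may be small. The rates in the illustration have no source in the documents, and eyes of one patient may not be independent. None of this touches the mismatch in the text.

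A reader might go further and infer that the day-of-surgery rule in item 6 deletes complications, because a patient is discontinued if both eyes cannot be randomized and operated per protocol. The documents do not support that. They say that the patient is discontinued, not that data already collected are discarded. It is unclear how a first-eye event that prevents surgery on the second eye would be reported, and that calls only for a clarification.

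**Conclusion.** The point holds as a conflict within the document. Complications by angle are an objective, while the readable plan has no complication variable and no complication comparison. The interim sentence can also lead to an undercount of postoperative events that resolve between visits. This conclusion rests on the wording alone.

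Three limits apply. The tick-box answer on a safety monitoring plan (Section 4, item 8) cannot be read in the supplied text, so nothing is concluded from it. The power and interval figures are illustrations on assumed rates and do not measure the defect. A reader might also infer that the trial gathers no safety information, or that the interim exclusion favours one angle. The first goes too far, because acuity and refraction carry some safety information. For the second the documents offer no evidence.

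**What to change.** 1. Add to the study variables in Section 4, item 9: intraoperative and postoperative complications, recorded per eye with type and date, from surgery through month 12 and including day 1. Fix the list of counted event types before any analysis by angle.
2. Amend the interim sentence in item 6. Interim acuity and refraction stay out of the visit-based analyses, but a complication documented at an interim examination is study data for that eye.
3. Report counts per angle and the paired risk difference with 95% CI, with and without interim-visit events. An exact McNemar test may be added. State that a non-significant result will not be read as no safety difference.
4. As a minor clarification, state that intraoperative events in patients discontinued on the day of surgery are kept and listed by angle, separately from the paired analysis. The discontinuation rule itself stays as it is.

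The cost is protocol wording, a per-eye event record, and abstraction from surgical and usual-care charts. No new scheduled visit is needed. The documents do not describe staffing, so the abstraction time cannot be estimated. The drawback is possible detection bias, because interim visits are discretionary and masking is described only for the patient. That is why the counts should be shown both ways.

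### Pre-op acuity is scheduled in both eyes but is not used as a covariate; adjusting each between-eye acuity test for it costs almost nothing and may narrow the interval

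*Combined protocol and SAP*

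**What the plan says.** The analysis is in section 4 (Study Information), item 9. The comparison of the two angles reads "Paired t-tests will be used to analyze the difference of corrected and uncorrected visual acuity obtained by each group at the post-op time points", and the sentence continues "as well as the average change from pre-op to post op corrected and corrected visual acuities". The second clause repeats one acuity type, presumably meaning corrected and uncorrected. It does not say whether change is compared between the two eyes or only described within each angle. No regression or covariate appears anywhere. The analysis times are set by "Statistics will be compiled for the one week, one month, three month, six month and 12 month time points post operatively", and the sample size by "a N number of 200 patients will be needed", with no effect size, SD, alpha or power.

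The baseline data are set in item 6 of the same section: "Uncorrected corrected visual acuity: Pre-op and post-op day 1, week 1, and months 1" (read here as uncorrected acuity) and "Best corrected visual acuity: Pre-op and post-op months 3", each continuing to later months. The same item says "All study outcome measures will be evaluated for both eyes at every visit". Item 1 classes the study as randomised, and item 6 discontinues patients if, on the day of surgery, "both eyes cannot be randomized and operated as per protocol".

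**The concern.** Every patient with both eyes measured before surgery will have a pre-op between-eye acuity difference. Because the eyes are randomised, that difference has expectation zero, so tests with and without adjustment for it estimate the same angle effect. If eyes that differ before surgery still tend to differ in the same direction afterwards, the post-op t-test leaves explainable variation in its error term. Raw change does use the baseline, but with the slope fixed at 1, which is efficient only if the true slope is near 1.

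At stake is the width of the confidence interval, not its validity. Since item 9 shows no basis for 200 patients, there is no demonstrated margin of precision to spare.

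**Working it through.** **Inputs from the documents.** 200 patients, hence 200 pairs of eyes (item 9); randomised eyes (items 1 and 6); both acuities scheduled pre-op (item 6). The figure of 200 cannot be reproduced because its inputs are not stated.

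**Assumed inputs.** r, the correlation between the pre-op and post-op between-eye differences: 0 to 0.5. Post-op between-eye SD: 0.08, 0.10 or 0.15 logMAR. True difference: 0.02 logMAR. Two-sided alpha: 5%. Pairing already removes variation between patients, so r concerns differences between eyes, not raw acuities.

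**Expected variance.** Adjusted relative to unadjusted, for a normal covariate with true mean zero: (1 - r²)(1 + 1/(n - 3)). At n = 200 and r = 0.3 this is 0.91 × (1 + 1/197) = 0.9146. The equivalent number of unadjusted pairs is 200/0.9146 = 219, and the interval width changes by √0.9146 - 1 = -4.4%.

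| r | Variance, 200 pairs | Equivalent pairs | CI width | Variance, 150 pairs |
|---|---|---|---|---|
| 0 | +0.5% | 199 | +0.3% | +0.7% |
| 0.15 | -1.8% | 204 | -0.9% | -1.6% |
| 0.3 | -8.5% | 219 | -4.4% | -8.4% |
| 0.5 | -24.6% | 265 | -13.2% | -24.5% |

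At 200 pairs the method breaks even at r = √(1 - 197/198) = 0.07.

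**Given a chance pre-op imbalance.** If the pre-op between-eye difference has t-statistic t, the ratio is (1 - r²)(1 + t²/(n - 1)). At t = 2 and 200 pairs the four changes become +2.0%, -0.3%, -7.2% and -23.5%, and break-even rises to r = 0.14. At t = 3 and r = 0 the cost is 9/199 = 4.5%.

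**Power** for 0.02 logMAR at 200 pairs (noncentral t):

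| Post-op between-eye SD | Unadjusted | Adjusted, r = 0.15 | r = 0.3 | r = 0.5 |
|---|---|---|---|---|
| 0.08 | 94% | 94% | 96% | 98% |
| 0.10 | 80% | 81% | 84% | 90% |
| 0.15 | 47% | 47% | 50% | 58% |

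**Simulation, normal data.** With 20,000 trials of 200 pairs at each r, the variance ratio was 1.004, 0.91 and 0.75 at r = 0, 0.3 and 0.5. The adjusted test's false-positive rate was 4.7% to 5.1%.

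**Simulation, acuities rounded to Snellen lines** (assumed models, 20,000 trials per case):

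- Corrected-like, r = 0.42: ratio 0.82-0.83 (formula 0.83); false positives 5.0% adjusted, 4.9% unadjusted; power 81% against 73%.
- Uncorrected-like, r = 0.13: ratio 0.99; false positives 5.1% and 5.2%; power 73% for both.
- Uncorrected-like, with 39% of pre-op eyes worse than 1.0 logMAR and coded 1.0, 1.3 or 1.9: ratio 0.993-0.995; false positives 5.0-5.2%. The code chosen barely matters there.

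**If change is also tested between eyes.** Let k be the ratio of the pre-op to the post-op SD of between-eye differences. The post-op and change tests then have correlation (1 - rk)/√(1 + k² - 2rk). If either test counted as a positive result, the false-positive rate per acuity per visit would be 7.2% (k = 0.5, r = 0.15) to 9.75% (k = 1.98, r = 0.5), both inputs assumed. Item 9 states no such rule, so this applies only under that reading.

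**The case against.** The strongest objection is that nothing is broken. Pairing already removes variation between patients, the t-test is valid, and item 9 answers a form that asks only for a summary. Every figure for the gain rests on an assumed r: at 0.15 power rises by at most about one point, and at 0 adjustment loses slightly. Five of the eight tests concern uncorrected acuity, where surgery removes most of what drove the pre-op value and the gain may be negligible. The favourable Snellen-rounded result shows that the formula holds on rounded data; it is not evidence that r is near 0.42 in this trial. All of that stands and limits what can be promised.

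Two further objections carry less weight. Replacing any between-eye test of change might seem to discard a planned analysis. But with the pre-op difference in the model, post-op value and change give the same angle effect, so nothing inferential is lost. The count of eight might be nine if day 1 is tested, because item 6 measures uncorrected acuity then. Item 9's own list of time points starts at week 1, and eight follows that list.

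**Conclusion.** The point holds as a low-cost improvement that should be made; it does not correct an error. The pre-op between-eye difference will be available, is unaffected by treatment and is used in no test as a covariate. Adjustment is worth nothing to about a quarter of the variance over r from 0 to 0.5. Its average cost is 0.5% if r is zero, or about 2% in a trial with a pre-op imbalance of t = 2. The documents cannot say where in that range the trial lies. A useful gain is more plausible for corrected than for uncorrected acuity. The conclusion does not depend on how the clause on change is read.

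**What to change.** In section 4, item 9:

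- State that acuity is analysed in logMAR, with one value fixed in advance for acuity too poor to read on the chart.
- At each analysed visit where that acuity is scheduled, regress the within-patient post-op difference (110 minus 70) on the within-patient pre-op difference (110 minus 70). The visits are week 1 and months 1, 3, 6 and 12 for uncorrected acuity, and months 3, 6 and 12 for corrected acuity.
- Do not centre the covariate at its sample mean; that would return the unadjusted estimate.
- Report the intercept with its 95% CI as the angle effect. Make it the only between-eye test for that acuity and visit, in place of separate post-op and change tests.
- Report change from pre-op descriptively by angle.

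This gives 5 + 3 = 8 tests. It does not name a primary acuity or visit, which is a separate matter. The cost is plan wording and one degree of freedom; no new data are needed. The wording should be fixed before outcomes are seen, so that the choice between adjusted and unadjusted results cannot follow the data.

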**3. Indicate any vulnerable participant groups (other than children) included:**

None

**If 'Other', please specify:****If 'None' and no children are involved, answer the following question.****Has the participant selection process overprotected potential subjects who are considered vulnerable so that they are denied opportunities to participate in research?** Yes  No**4. Number of participants to be included and/or enrolled in this entire study, across all study locations:** 200**At Utah prior to October 2019:** 200**5. Characteristics of Participants/Inclusion Criteria:**

Subjects who are deemed suitable candidates for bilateral LASIK will be considered eligible for participation in this study. Correction will be distance for both eyes. Patients must be at least 21 years of age.

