**List by name, role, and affiliation any others who will obtain consent (e.g. [name], Co-Investigator, etc.).**

**2. Describe the location(s) where consent will be obtained.**

Moran Eye Center Clinics

**3. Describe the consent process(es), including the timing of consent. Describe whether there is a waiting period between the consent process and obtaining consent from the participant (i.e., any time between informing participants and actually obtaining consent).**

Consent will be obtained following standard of care evaluations that determine if an individual is a candidate for bilateral LASIK surgery. This occurs during a series of pre-operative clinic visits. Signed consent will be obtained prior to surgery.

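### The reason given for 200 patients is not a sample-size basis, and none of at least eight planned acuity tests is named as primary

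*Combined protocol and SAP*

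**What the plan says.** Section 4 (Study Information), item 9 carries the instruction "Factors for determining the proposed sample size (e.g., power) should be stated". The answer ends: "In order to provide a statistically significant beta values, a N number of 200 patients will be needed". It gives no significance level, power, target difference, SD of the paired difference or loss allowance, and section 9 lists no separate full protocol.

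The same item sets the analysis. On visits: "Statistics will be compiled for the one week, one month, three month, six month and 12 month time points post operatively". On tests: "Paired t-tests will be used to analyze the difference of corrected and uncorrected visual acuity obtained by each group at the post-op time points". Tests of change from pre-op are added. No measure or visit is ranked above another there, and Study Purposes and Objectives lists the two acuities and the complications without ranking.

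The procedure list in section 4, item 6 schedules uncorrected acuity at day 1, week 1 and months 1, 3, 6 and 12, and best corrected acuity at months 3, 6 and 12. The text above that list says that every outcome measure is assessed at every visit, which does not agree with the list.

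On numbers, section 3 (Participants), item 4 gives 200 for "Number of participants to be included and/or enrolled in this entire study, across all study locations". Section 4.2, item 3 says "Signed consent will be obtained prior to surgery". Section 4, item 6 foresees two routes of loss, neither with a rate: "Patients will be discontinued from the study if, on the day of surgery, both eyes cannot be randomized and operated as per protocol" and "Patients have the right to withdraw at any time and future medical care will not be influenced by their lack of participation".

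**The concern.** The reason given for 200 does not fit the analysis. No regression is planned, so there is no coefficient to be significant. If beta means the type II error rate, it is chosen beforehand and is not tested. A reader cannot tell which comparison the 200 patients serve, or what difference the trial could detect.

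The missing primary comparison matters more. The Background says that outcomes and complication rates are meant to help in choosing between the angles. Each paired t-test is valid alone. But with several measures and visits on an equal footing, one significant visit could be presented as the finding even if the angles do not differ. No confidence interval is planned either, so a non-significant test could be read as showing no difference.

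**Working it through.** **1. Can 200 be reproduced?** No. The inputs that a paired t-test calculation needs (significance level, power, SD of the paired difference, target difference) are all absent. Only back-calculation is possible. It uses the noncentral t with n − 1 degrees of freedom and noncentrality d√n, where d is the mean between-eye difference divided by its SD, at an assumed two-sided 5%:

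- d = 0.20, 80% power: 199 pairs (power 0.8017; 198 pairs give 0.7997).
- d = 0.23, 90% power: 201 pairs (power 0.9006; 200 pairs give 0.8992).

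So 200 is close to at least two conventional cases. The documents state neither, and this is not a reproduction.

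**2. Does 200 provide significance?** With 200 pairs, the chance of a significant result is 5%, 29%, 80% and 99% for true differences of 0, 0.1, 0.2 and 0.3 SD. It depends on the true difference, which is not given.

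**3. How many tests?** Take the visits in item 9 and the schedule in item 6.

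- Uncorrected acuity: week 1 and months 1, 3, 6, 12 = 5.
- Best corrected acuity: months 3, 6, 12 = 3.
- Total 5 + 3 = 8, before the change-from-pre-op tests.

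If all measures were taken at every visit, as item 6 also says, the five analysed visits would give 5 × 2 = 10. Eight is therefore a minimum.

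**4. Chance of at least one significant test if the angles are alike** (two-sided 5% for each of eight tests). Under independence: 1 − 0.95⁸ = 0.337. Repeated acuities in the same patients will be correlated, so I also simulated eight multivariate normal test statistics (400,000 runs per row). The correlations are assumptions.

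| Same-measure correlation | Cross-measure correlation | At least one significant |
|---|---|---|
| 0 | 0 | 34% |
| 0.5 | 0.2 | 28% |
| 0.7 | 0.3 | 23% |
| 0.9 | 0.3 | 17% |
| 0.9 | 0.8 | 14% |
| One named primary | – | 5% |

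The last two simulated rows show that the cross-measure correlation matters as well: at 0.9 within measure, the figure moves from 17% to 14%.

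**5. What 200 enrolled delivers.** Loss rates are assumptions; both eyes must be measured. The CI half-width, in SD of the between-eye difference, is t(0.975, n − 1)/√n.

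| Loss | Pairs | Power at 0.2 SD | Detectable at 80% power | 95% CI half-width |
|---|---|---|---|---|
| 0% | 200 | 80% | 0.199 SD | 1.972/√200 = 0.139 SD |
| 10% | 180 | 76% | 0.210 SD | 1.973/√180 = 0.147 SD |
| 20% | 160 | 71% | 0.223 SD | 1.975/√160 = 0.156 SD |

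If 200 complete pairs were intended, enrolment would have to be 200/0.9 = 222.2, so 223, or 200/0.8 = 250.

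**The case against.** The strongest reply is that this is a short ethics-board form for a study using standard-of-care procedures, and that the beta phrase is clumsy shorthand for adequate power, since the prompt mentions power. On that reading, showing that 200 pairs do not guarantee significance rebuts only the literal wording. This is fair. But shorthand for power still needs a power level, a difference and an SD, and none is given. The form asked for them, and the study is declared a randomized trial with hypothesis tests.

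A reader might infer that 200 is too small. The documents do not support that: 200 fits a conventional target about as well as any number could, and no stated input contradicts it.

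A reader might also infer that the plan contradicts itself by needing 200 and enrolling 200 while foreseeing losses. That goes too far. Item 9 speaks of patients, not complete pairs, and the field in section 3 covers included and/or enrolled. Both can simply mean recruit 200. No loss rate is given, and whether patients discontinued on the day of surgery count toward the 200 or are replaced is not stated. Only if 200 means complete pairs do the foreseen losses leave fewer than needed. What stands is that the meaning should be stated.

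On multiplicity, independence is implausible for repeated measures in the same patients, so 34% should not be quoted alone. The harm also depends on one visit being singled out, which the plan does not propose. But nothing in the plan prevents it, and even strong assumed correlations leave the chance well above 5%.

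**Conclusion.** The concern holds in this form: the stated reason for 200 is not a sample-size basis for paired t-tests, 200 cannot be reproduced, and at least eight between-eye acuity tests have no primary among them. If the angles are alike, the chance of at least one significant acuity test is roughly 14% to 34%, against 5% with one primary. The range rests on an assumed two-sided 5% per test and assumed correlations; the count of eight rests on the item 6 list.

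This is a missing justification and a missing primary comparison, not a calculation shown to be wrong. It does not establish that 200 is inadequate, nor that enrolment falls short of need. It concerns acuity only; the sample size is not tied to complications either. The change should be made, but each planned test remains valid on its own.

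**What to change.** Before acuity by angle is seen, replace the sample-size sentence in section 4, item 9 with text along these lines:

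> The primary comparison is the paired mean difference (70 minus 110 degrees) in uncorrected visual acuity at 3 months, Snellen converted to logMAR, by paired t-test at two-sided 5%, with its 95% CI. All other acuity comparisons are secondary and reported as paired mean differences with 95% CIs. A non-significant test will not be reported as no difference. 200 patients will be enrolled. If 10% to 20% lack both eyes measured at 3 months, 180 to 160 pairs give 80% power for a mean difference of 0.21 to 0.22 SD of the between-eye difference, with a 95% CI of about ±0.15 to ±0.16 SD.

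The measure, visit and logMAR scale are a suggested default. Uncorrected acuity comes first in the stated objectives and is scheduled at every analysed visit, and month 3 is the first visit at which the item 6 list has both acuities. The sponsor may name another acuity measure or visit; the SD-unit figures hold for the same number of pairs.

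The sponsor should add its own SD of the between-eye difference, because SD units alone do not show whether the detectable difference matters in acuity terms. It should confirm in section 3, item 4 that 200 is the number enrolled, and reconcile the two statements in item 6 about which measures are taken at which visit.

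The cost is a protocol amendment. The sponsor commits to one measure, scale and visit, can no longer promote another significant visit to the main result, and states slightly less favourable precision than 200 complete pairs would give. No extra visits or patients are needed; 23 to 50 more would be enrolled only if 200 complete pairs are wanted at 10% to 20% loss.
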